### **8.1.3. Biomarker Efficacy Measures**

Biomarker efficacy measures collected in this study are described in the respective sections below:

- Florbetapir F 18 PET scan – Section 8.6.1
- Flortaucipir F 18 PET scan – Section 8.8
- Volumetric MRI – Section 8.8

## **8.2. Safety Assessments**

Planned time points for all safety assessments are provided in the SoA.

### **8.2.1. Physical and Neurological Examinations**

Complete and brief physical examinations will be performed as indicated in the SoA (Section 1.3).

The complete physical examination will include assessment of the following:

- general appearance;
- skin, head, and neck;
- lymph nodes;
- thyroid;
- abdomen (bowel sounds, liver and spleen palpation);
- back (costovertebral angle tenderness); and
- musculoskeletal, cardiovascular, and respiratory systems.

The brief physical examination will include assessments of the following:

- skin,
- lungs,
- cardiovascular system, and
- abdomen (bowel sounds, liver and spleen palpation).

Complete neurological examinations will be performed as indicated in the SoA (Section 1.3).

The examinations will include a thorough assessment of the following:

- gait,
- balance,
- coordination,
- cranial nerves,
- sensory and motor systems, and
- reflexes.

If necessary, given the training of the PI, a neurologist may be consulted in the event of significant new findings.

If a clinically meaningful change in an MRI is noted during the study, an additional full neurological exam should be performed as soon as possible, along with any other medical follow-up deemed necessary by the investigator.

### **8.2.2. Vital Signs**

Vital signs, including temperature, will be measured as indicated in the SoA (Section 1.3).

Vital signs should be taken before administration of IP. Vital signs may be repeated as needed.

#### **8.2.2.1. Blood Pressure**

Sitting blood pressure and pulse will be measured after 5 minutes in the sitting position at all visits. In addition, orthostatic blood pressure and pulse will be measured supine and standing at designated visits, as detailed in the SoA (Section 1.3).

For orthostatic blood pressure monitoring, participants should be supine for at least 5 minutes and then stand for at least 3 minutes prior to taking the respective measurements. If the subject feels unable to stand, only supine vital signs will be recorded.

Unscheduled orthostatic vital signs should be assessed, if possible, during any AE of dizziness or posture-induced symptoms.

Any clinically significant findings from vital sign measurements that result in a diagnosis and that occur after the participant receives the first dose of study treatment should be reported to Lilly or its designee as an AE via CRF/electronic data entry.

#### **8.2.2.2. Height, Weight, and Body Temperature**

Height and body weight will be measured. Measurements should be taken, when possible, with the same scale for all measurements. Body mass index will be calculated from the height and body weight.

Temperature will be recorded using an oral or tympanic (or other acceptable route) thermometer.

Any body weight data entered into the CRF will be used for the overall data analysis.

### **8.2.3. Electrocardiograms**

12-lead digital ECGs will be collected according to the SoA (Section 1.3). Participants must be supine for approximately 5 to 10 minutes before ECG collection and remain supine but awake during ECG collection.

ECGs may be obtained at additional times, when deemed clinically necessary. Collection of more ECGs (replicates) than expected at a time point is allowed when needed to ensure high-quality records.

ECGs will initially be interpreted by a qualified physician (the investigator or qualified designee) at the site as soon after the time of ECG collection as possible, and ideally while the participant is still present, to determine whether the subject meets entry criteria at the relevant visit(s) and for immediate participant management, should any clinically relevant findings be identified.

After enrollment, if a clinically significant increase in the QT/QTc interval from baseline or other clinically significant quantitative or qualitative change from baseline is identified, the

participant will be assessed by the investigator for symptoms (e.g., palpitations, near syncope, syncope) and to determine whether the participant can continue in the study. The investigator or qualified designee is responsible for determining if any change in participant management is needed. The investigator or qualified designee must document his/her review of the ECG printed at the time of evaluation.

All digital ECGs will be electronically transmitted to a designated central ECG laboratory. A cardiologist at the central ECG laboratory will then conduct a full overread. A report based on data from this overread will be issued to the investigative site. These data are not routinely reported back to the investigative site. All data from the overreads will be placed in the Lilly database for analytical and study report purposes.

When there are differences in ECG interpretation between the investigator (or qualified designee) and the cardiologist at the central ECG laboratory, the investigator's (or qualified designee's) interpretation will be used for study entry and immediate participant management. Interpretations from the cardiologist at the central ECG laboratory will be used for data analysis and report writing purposes.

The investigator (or qualified designee) must document his/her review of the ECG printed at the time of collection, the final overread ECG report issued by the central ECG laboratory, and any alert reports.

#### **8.2.4. Clinical Safety Laboratory Assessments**

See Section 10.2 for the list of clinical laboratory tests to be performed and to the SoA for the timing and frequency.

The investigator must review the laboratory report, document this review, and record any clinically relevant changes occurring during the study in the AE section of the CRF. The laboratory reports must be filed with the source documents. Clinically significant abnormal laboratory findings are those which are not associated with the underlying disease, unless judged by the investigator to be more severe than expected for the participant's condition.

All laboratory tests with values considered clinically significantly abnormal during participation in the study, or within the follow-up period after the last dose of IP, should be repeated until the values return to normal, baseline, or are no longer considered clinically significant by the investigator or medical monitor.

1. If such values do not return to normal/baseline within a period of time judged reasonable by the investigator, the etiology should be identified and the sponsor notified.
2. All protocol-required laboratory assessments, as defined in Section 10.2, must be conducted in accordance with the laboratory manual and the SoA.
3. If laboratory values from nonprotocol-specified laboratory assessments performed at the institution's local laboratory require a change in participant management or are considered clinically significant by the investigator (for example, SAE, AE, or dose modification), then the results must be recorded in the CRF.

Lilly or its designee will provide the investigator with the results of laboratory tests analyzed by a central vendor, if a central vendor is used for the clinical trial.

Any clinically significant findings from laboratory tests that result in a new diagnosis and that occur after the participant receives the first dose of IP should be reported to Lilly or its designee as an AE via CRF/electronic data entry.

### 8.2.5. Magnetic Resonance Imaging

MRI of the brain will be performed according to the SoA (Section 1.3) and as clinically indicated. Unscheduled MRIs may be performed at the discretion of investigator.

This technology will be used to check for evidence of ARIA-H or ARIA-E and safety findings (volumetric MRI will also be used to calculate brain volumes, as noted in Section 8.8).

The MRI scans will be reviewed by the investigator or qualified designee for immediate participant management. Any clinically significant findings noted that result in a new or updated diagnosis should be recorded as an AE. After the MRI scan is read locally, the MRI scans will be sent for analysis to a centralized MRI vendor designated by Lilly. The centralized MRI vendor's interpretation of the participant's final MRI from the originating study or unscheduled MRI performed in Study AACH prior to Part B will determine final MRI eligibility for Part B.

Specific analyses of the scans, including assessments of ARIA-H and ARIA-E and calculations of brain volumes, will be interpreted by the centralized MRI vendor for data analysis and report writing purposes.

Results of centrally read MRIs regarding participant care/safety will be reported back to sites.

### 8.2.6. Hepatic Safety Monitoring

#### Close Hepatic Monitoring

Laboratory tests (Section 10.4), including ALT, AST, ALP, TBL, direct bilirubin, GGT, and CK, should be repeated within 48 to 72 hours to confirm the abnormality and to determine if it is increasing or decreasing, if 1 or more of these conditions occur:

If a participant with baseline results of ...	develops the following elevations:
ALT or AST <1.5x ULN	ALT or AST $\geq$ 3x ULN
ALP <1.5x ULN	ALP $\geq$ 2x ULN
TBL <1.5x ULN	TBL $\geq$ 2x ULN (except for participants with Gilbert's syndrome)
ALT or AST $\geq$ 1.5x ULN	ALT or AST $\geq$ 2x baseline
ALP $\geq$ 1.5x ULN	ALP $\geq$ 2x baseline
TBL $\geq$ 1.5x ULN	TBL $\geq$ 2x baseline (except for participants with Gilbert's syndrome)

Abbreviations: ALP = alkaline phosphatase; ALT = alanine aminotransferase; AST = aspartate aminotransferase; TBL = total bilirubin level; ULN = upper limit of normal.

If the abnormality persists or worsens, clinical and laboratory monitoring, and evaluation for possible causes of abnormal liver tests should be initiated by the investigator in consultation with the Lilly-designated medical monitor. At a minimum, this evaluation should include physical examination and a thorough medical history, including symptoms, recent illnesses (for example: heart failure, systemic infection, hypotension, or seizures), recent travel, history of concomitant

medications (including over-the-counter), herbal and dietary supplements, and history of alcohol drinking and other substance abuse.

Initially, monitoring of symptoms and hepatic biochemical tests should be done at a frequency of 1 to 3 times weekly, based on the participant's clinical condition and hepatic biochemical tests. Subsequently, the frequency of monitoring may be lowered to once every 1 to 2 weeks if the participant's clinical condition and laboratory results stabilize. Monitoring of ALT, AST, ALP, and TBL should continue until levels normalize or return to approximate baseline levels.

#### Comprehensive Hepatic Evaluation

A comprehensive evaluation should be performed to search for possible causes of liver injury if 1 or more of these conditions occur:

If a participant with baseline results of...	develops the following elevations:
ALT or AST <1.5x ULN	ALT or AST $\geq$ 3x ULN with hepatic signs/symptoms*, or ALT or AST $\geq$ 5x ULN
ALP <1.5x ULN	ALP $\geq$ 3x ULN
TBL <1.5x ULN	TBL $\geq$ 2x ULN (except for participants with Gilbert's syndrome)
ALT or AST $\geq$ 1.5x ULN	ALT or AST $\geq$ 2x baseline with hepatic signs/symptoms*, or ALT or AST $\geq$ 3x baseline
ALP $\geq$ 1.5x ULN	ALP $\geq$ 2x baseline
TBL $\geq$ 1.5x ULN	TBL $\geq$ 1.5x baseline (except for participants with Gilbert's syndrome)

Abbreviations: ALP = alkaline phosphatase; ALT = alanine aminotransferase; AST = aspartate aminotransferase; TBL = total bilirubin level; ULN = upper limit of normal.

\* Hepatic signs/symptoms are severe fatigue, nausea, vomiting, right upper quadrant abdominal pain, fever, rash, and/or eosinophilia >5%.

At a minimum, this evaluation should include physical examination and a thorough medical history, as outlined above, as well as tests for Prothrombin time and INR; tests for viral hepatitis A, B, C, or E; tests for autoimmune hepatitis; and an abdominal imaging study (for example, ultrasound or CT scan).

Based on the participant's history and initial results, further testing should be considered in consultation with the Lilly-designated medical monitor, including tests for hepatitis D virus, cytomegalovirus, Epstein-Barr virus, acetaminophen levels, acetaminophen protein adducts, urine toxicology screen, Wilson's disease, blood alcohol levels, urinary ethyl glucuronide, and serum phosphatidylethanol. Based on the circumstances and the investigator's assessment of the participant's clinical condition, the investigator should consider referring the participant for a hepatologist or gastroenterologist consultation, magnetic resonance cholangiopancreatography, endoscopic retrograde cholangiopancreatography, cardiac echocardiogram, or a liver biopsy.

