ADAS-Cog 13			X			X			X			X			X	X	X	X	X		X		Administer the ADAS-Cog 13 , ADCS-ADL, CDR-SB, and MMSE prior to medical procedures that could be stressful to the participant (blood draws, etc.; Section 8.1.2). These tests include the audio voice recording of the rater's questions and the participant and study partner responses to assessment questions.	
ADCS-ADL			X			X			X			X			X	X	X	X	X		X			
CDR-SB (Global Sum of Boxes - CDR)			X			X			X			X			X	X	X	X	X		X			
MMSE			X			X			X			X			X	X	X	X	X		X			
Clinician-Administered Assessments (Paper)																								
C-SSRS Screening/Baseline			X																					

		Part B: Open-Label																	Part B: Follow-Up, UV, ED				Comments	
		1	2	3	4	5	6	7	8	9	10	11 c	12 c	13 c	14 c	15	801 d	802 d	UV	ED				
Visit Number	UP b	1	2	3	4	5	6	7	8	9	10	11 c	12 c	13 c	14 c	15	801 d	802 d	UV	ED	ED only if participant has completed V1 and received IP in Part B.			
Weeks Relative to Baseline (V1)		0	4	8	12	16	20	24	28	32	36	40	44	48	60	72	84	96	997			Procedures for some visits may take more than 1 day.		
Visit Interval Tolerance (days)		—	-7 to +10	±7	±7	±7	±7	±7	±7	±7	±7	±7	±7	±7	±7	±7	±7	±7	±7					
C-SSRS Since Last Visit			X	X	X	X	X	X	X	X	X	X	X	X	X	X	X	X	X	X	X			
Self-Harm Supplement Form			X	X	X	X	X	X	X	X	X	X	X	X	X	X	X	X	X	X	X			
Self-Harm Follow-Up Form			X	X	X	X	X	X	X	X	X	X	X	X	X	X	X	X	X	X	X	Required if triggered by the Self-Harm Supplement Form per instructions.		
Laboratory Tests and Sample Collectionsf																								
Hematology		X	X	X	X	X			X			X			X	X						X	Labs at V14 not required for participants who completed dosing at V10. Perform prior to V1 at UP if last recorded labs from the originating study were collected >6 months before V1.	
Clinical Chemistry		X	X	X	X	X			X			X			X	X						X		
P-tau			X			X			X			X			X	X	X	X	X		X			
NfL			X			X			X			X			X	X	X	X	X		X			
Aβ			X			X			X			X			X	X	X	X	X		X			

		Part B: Open-Label																Part B: Follow-Up, UV, ED				Comments	
		Visit Number	UP b	1	2	3	4	5	6	7	8	9	10	11 c	12 c	13 c	14 c	15	801 d	802 d	UV	ED	
Weeks Relative to Baseline (V1)		0		4	8	12	16	20	24	28	32	36	40	44	48	60	72	84	96	997			Procedures for some visits may take more than 1 day.

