- c V11 and V12 do not occur for participants with a final dose at or before V10. Participants resume the visit schedule with V13 (Week 48). V14 may be optional for some participants, as determined by the sponsor.
- d Follow-up visits are not required if the participant meets release requirements determined by the sponsor.
- e For Part B ED visit, collect florbetapir F 18 PET scan only if a florbetapir F 18 PET scan has not yet been performed and participant has received at least 3 doses of donanemab.
- f Unscheduled lab tests may be performed at the discretion of the investigator. Collect labs prior to administration of IP, unless otherwise noted.
- g Perform the flortaucipir F 18 and florbetapir F 18 PET scans  $\geq$ 16 hours apart from each other.

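### Protocol 8.2.6: for raised baseline bilirubin, the full liver work-up triggers at 1.5x baseline but the 48 to 72 hour repeat test only at 2x baseline

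*Protocol*

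**What the plan says.** Protocol Section 8.2.6 sets two levels of response to abnormal liver tests.

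- **Close Hepatic Monitoring.** When a trigger in its table is met, the liver panel "should be repeated within 48 to 72 hours to confirm the abnormality and to determine if it is increasing or decreasing". If the abnormality persists or worsens, "monitoring of symptoms and hepatic biochemical tests should be done at a frequency of 1 to 3 times weekly" to begin with.
- **Comprehensive Hepatic Evaluation.** "A comprehensive evaluation should be performed to search for possible causes of liver injury if 1 or more of these conditions occur". The minimum content is examination, history, prothrombin time and INR, viral and autoimmune hepatitis tests, and abdominal imaging.

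Both tables have the same six rows, defined by whether baseline ALT/AST, ALP or TBL is below 1.5x ULN or at or above it. For baseline TBL at or above 1.5x ULN, the comprehensive table reads "TBL $\geq$ 1.5x baseline (except for participants with Gilbert's syndrome" and the close-monitoring table reads "TBL $\geq$ 2x baseline (except for participants with Gilbert's syndrome". Neither table explains the difference.

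Two other provisions bear on retesting. Section 8.2.4 says that values judged clinically significantly abnormal "should be repeated until the values return to normal, baseline, or are no longer considered clinically significant by the investigator or medical monitor". Footnote f to the Schedule of Activities says "Unscheduled lab tests may be performed at the discretion of the investigator".

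**The concern.** A quick confirmatory repeat is the smaller action and would normally be triggered no later than a full search for causes of liver injury. In this one row the order is reversed. A participant with an isolated bilirubin rise between 1.5x and 2x baseline is sent for serology and imaging, but nothing in 8.2.6 requires a prompt check that the value is real or a reading of its direction.

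What is at stake is participant monitoring. In that band, the only retest with a fixed date is the next scheduled chemistry sample, and infusions continue every 4 weeks until then unless the investigator intervenes.

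**Working it through.** No statistical calculation is involved. The check is a row-by-row comparison of the two tables in 8.2.6, followed by the width of the uncovered band and the time to the next fixed sample.

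**1. Row comparison** (bl = baseline)

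| Baseline row | Repeat trigger | Work-up trigger | Order |
|---|---|---|---|
| ALT/AST <1.5x ULN | 3x ULN | 3x ULN with symptoms, or 5x ULN | ordered |
| ALP <1.5x ULN | 2x ULN | 3x ULN | ordered |
| TBL <1.5x ULN | 2x ULN | 2x ULN | equal |
| ALT/AST ≥1.5x ULN | 2x bl | 2x bl with symptoms, or 3x bl | ordered |
| ALP ≥1.5x ULN | 2x bl | 2x bl | equal |
| TBL ≥1.5x ULN | 2x bl | 1.5x bl | **inverted** |

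Three rows are ordered, two are equal and one is inverted. Both TBL rows except Gilbert's syndrome in both tables.

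**2. Width of the band.** For a baseline of b (in multiples of ULN, b ≥ 1.5), the work-up but not the repeat is triggered from 1.5b to just under 2b. The protocol gives no distribution of baseline values, so the values of b above 1.5 are illustrative.

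- b = 1.5: 1.5 × 1.5 = 2.25, and 2 × 1.5 = 3.0. The band is 2.25x to <3.0x ULN.
- b = 2.0: the band is 3.0x to <4.0x ULN.
- b = 2.5: the band is 3.75x to <5.0x ULN.

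This assumes an isolated rise. If ALT, AST or ALP meets its own trigger, the repeat panel is required anyway and includes bilirubin.

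**3. Effect at the 1.5x ULN baseline cut.** Take an on-study TBL of 2.8x ULN. With a baseline of 1.4x ULN the repeat is required, since 2.8 ≥ 2. With a baseline of 1.5x ULN it is not, since 2.8 / 1.5 = 1.87, which is below 2. In both cases the work-up is required (2.8 ≥ 2, and 1.87 ≥ 1.5).

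**4. Does other text supply the timed repeat?**

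- Section 8.2.4 asks for repeats, but only of values judged clinically significant, and it sets no interval.
- Footnote f to the Schedule of Activities is permissive.
- Appendix 4 (Section 10.4) lists total and direct bilirubin in the hepatic panel without timing.
- The liver criteria for stopping study drug in Section 7.1 use bilirubin only in combination with ALT/AST or ALP, so an isolated rise does not meet them.

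**5. Time to the next fixed sample.** Allowing for the broken table, the Part B chemistry row reads as Visits 1, 2, 3, 4, 7, 10, 13 and 14, that is Weeks 0, 4, 8, 12, 24, 36, 48 and 60. The interval is 4 weeks up to Week 12 and 12 weeks after that. From Week 12 to Week 24 it is 12 × 7 = 84 days. With ±7 days at each end it is 70 to 98 days, against 2 to 3 days for the repeat. Infusions are scheduled at Weeks 16 and 20 in between. The Week 60 sample is not universal: "Labs at V14 not required for participants who completed dosing at V10". For those participants Week 48 appears to be the last scheduled chemistry, apart from an early discontinuation visit.

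**6. Effect on the SAP.** SAP Section 7.6.2 counts total bilirubin at or above 2x ULN at any time. The lowest value in the band is 2.25x ULN, so everyone in it is already counted. No SAP category needs to change.

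**The case against.** The strongest case on the other side is that this is a table inconsistency with little practical effect.

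- **Retesting would probably happen anyway.** The work-up already requires fresh blood, and the Appendix 4 panel includes bilirubin. A value that has prompted a search for liver injury would be hard to dismiss as clinically insignificant under 8.2.4. The investigator or medical monitor can stop study drug on clinical judgment under 7.1. This stands as a limit on the likely harm. It does not supply the interval or the serial schedule that the other rows give.
- **The inversion errs toward caution.** The larger action comes earlier, no work-up is lost, and a site can comply with both tables. This also stands.
- **The group may be empty.** It needs baseline TBL of at least 1.5x ULN without Gilbert's syndrome, in someone not kept out of Part B by exclusion criterion 13 or from dosing by the note in 7.2, followed by an isolated rise in the band. The documents give no count, and very few participants is the likely answer.
- **The jump at the baseline cut is not peculiar to bilirubin.** The ALP repeat trigger also moves from 2x ULN to 2 × 1.5 = 3.0x ULN. That is correct, so the jump alone is not the fault. The ALP work-up trigger is 3.0x ULN on both sides of the cut, so ALP never inverts. The bilirubin work-up trigger moves only from 2.0x to 2.25x ULN, so bilirubin does.
- **The documents do not show which cell is wrong.** All three raised-baseline rows of the close-monitoring table read 2x baseline, so the comprehensive cell could be the slip. This stands, and it favours a correction that is safe either way.

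**Conclusion.** The concern holds. One of the six rows is inverted, and for an isolated TBL rise of 1.5x to under 2x baseline no other provision supplies a timed repeat. At a baseline of 1.5x ULN the uncovered band is 2.25x to under 3.0x ULN, and it widens in proportion to baseline. The longest usual wait for a fixed sample between Weeks 12 and 48 is about 12 weeks.

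The consequence is confined to safety monitoring of a probably very small group, and many investigators would retest unprompted. No efficacy analysis, power figure or SAP hepatic category is affected. It should be corrected at the next amendment, but it does not threaten the trial's conclusions.

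The conclusion rests on the chemistry schedule as read from the Part B table, and on the rise being isolated.

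**What to change.** In the Close Hepatic Monitoring table, change the trigger in the last row (baseline TBL at or above 1.5x ULN) from 2x baseline to 1.5x baseline, and keep the Gilbert's exception. Leave the comprehensive table as it is. The six rows then stand at three ordered, three equal and none inverted. At a baseline of 1.5x ULN, both actions trigger at 2.25x ULN.

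This works whichever cell was the mistake, because it only adds a repeat test. If the sponsor's hepatic safety group intended a higher threshold for the work-up, it can raise that cell afterwards without recreating the inversion.

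The cost is one table cell at the next amendment, a note to sites, and a few extra blood tests. No SAP change is needed.
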